8.1.3. Efficacy Assessments

8.1.3.1. Antiviral Efficacy and Immunologic Change

Blood samples for determination of plasma HIV-1 RNA viral load and immunologic parameters will be taken at the time points specified in the Schedule of Activities (SoA).

Plasma viral load will be measured using a validated assay at a central laboratory (ie, Roche COBAS AmpliPrep/COBAS TaqMan HIV-1 Test, Version 2.0.) The assay linear range is 20 to 10,000,000 copies/mL with a lower limit of quantification (LLOQ) of 20 copies/mL and a limit of detection (LOD) of 20 copies/mL). Immunologic change will be determined by changes in CD4⁺ cell count (absolute and %).

Changes in viral load, changes in CD4⁺ cell counts (either decreases or increases) or detected resistance will be part of the efficacy analysis and should not be reported as AEs or SAEs.

8.1.3.2. Resistance Determinations

Samples for HIV-1 genotype/phenotype resistance testing (PhenoSense GT® Plus Integrase) will be taken at the time points specified in the Schedule of Activities (SoA).

For participants with confirmed virologic rebound (2 consecutive HIV-1 RNA values ≥200 copies/mL at a scheduled or unscheduled visit) and with a HIV-1 RNA value ≥400 copies/mL, HIV-1 genotypic/phenotypic resistance testing will be performed on the confirmed rebound sample if HIV-1 RNA ≥400 copies/mL or on a following visit with HIV-1 RNA ≥400 copies/mL. Other time points may still be analyzed if deemed necessary by the sponsor. For further details on the management of virologic rebound, see Appendix 13: Management of Virologic Rebound. Whole blood samples will be taken for storage and will be analyzed if deemed necessary by the sponsor to characterize archived viral resistance (GenoSure Archive®).

8.1.3.3. Management of Virologic Rebound

Participants with HIV-1 RNA ≥200 copies/mL will be managed as follows:

- If a single viral load measurement is ≥200 copies/mL after having previously been <50 copies/mL, participants should be contacted preferably within 48 hours to assess potential causes (eg, active substance abuse, depression, other intercurrent illnesses, lack of adherence) and adequate intervention should be provided (eg, additional adherence counseling). HIV-1 RNA testing should be repeated at a scheduled or unscheduled visit 2 to 4 weeks after the date of the initial viral load result of HIV-1 RNA ≥200 copies/mL.
- Upon confirmation of HIV-1 RNA ≥200 copies/mL, potential causes of virologic rebound should be documented. Assessment should include adherence, concomitant medication, and comorbidities (eg, active substance abuse, depression, other intercurrent illnesses, lack of adherence).
- If virologic rebound is confirmed at the scheduled or unscheduled visit and the HIV-1 RNA value is ≥400 copies/mL, the blood sample from that visit or a following visit with HIV-1 RNA ≥400 copies/mL will be used for HIV-1 genotypic and phenotypic testing (using PhenoSense GT[®] Plus Integrase).
- If genotypic/phenotypic resistance to study intervention is determined, study intervention may be discontinued at the discretion of the investigator. In case of early discontinuation, and HIV-

61

1 RNA ≥400 copies/mL, an HIV-1 genotypic/phenotypic resistance report, if available, will be forwarded to the investigator and/or participant's primary care provider in order to assist in the selection of a new ARV regimen.

• If no resistance is detected from genotypic/phenotypic resistance testing, the participant may remain on study intervention and the viral load will be further monitored. Genotypic/phenotypic resistance testing at other time points may be requested if deemed necessary by the sponsor. Investigators should carefully evaluate the benefits and risks of remaining on study intervention for each individual participant and document this assessment in the on-site medical record. Investigators who opt to discontinue study intervention for an individual participant must discuss this with the sponsor's medical monitor prior to study intervention discontinuation.

Evaluations may be performed at other time points at the sponsor's discretion. Additional exploratory resistance assays may be performed. A schematic overview of the guidance for management of participants who meet the criteria for virologic rebound is provided in Appendix 13: Management of Virologic Rebound.

8.1.4. Adherence

Treatment adherence for the study will be assessed by participant self-report using a 4-day recall for D/C/F/TAF FDC and participants receiving an INI + TAF/FTC ARV regimen at the time points specified in the Schedule of Activities (SoA).

8.2. Safety Assessments

Adverse events will be reported and followed by the investigator as specified in Section 8.3, Adverse Events and Serious Adverse Events and Appendix 4: Adverse Events: Definitions and Procedures for Recording, Evaluating, Follow-up, and Reporting.

Special attention will be paid to those participants who discontinue the study for an AE, or who experience severe (Grade 3) or potentially life-threatening (Grade 4) AEs, or SAEs. For reported HIV events, further details will be recorded if these events are AIDS-defining illnesses (World Health Organization Clinical Staging of HIV/AIDS, located in Appendix 12: WHO Clinical Staging of HIV/AIDS. For participants with specific adverse events, toxicity management should be done as described in Section 8.2.6.

Any clinically relevant changes occurring during the study must be recorded on the AE section of the CRF. Clinical events and clinically significant laboratory abnormalities will be graded according to the Division of AIDS (DAIDS) as specified in Appendix 7: DAIDS Table for Grading the Severity of Adult and Pediatric Adverse Events. Any clinically significant abnormalities persisting at the end of the study/early withdrawal will be followed by the investigator until resolution or until a clinically stable condition is reached. All Grade 3 and Grade 4 laboratory abnormalities and all laboratory abnormalities resulting in an increase of 2 DAIDS grades from baseline will be followed until return to baseline or within 1 grade from baseline (ie, ≤Grade 2). The study will include evaluations of safety and tolerability according to the time points provided in the Schedule of Activities (SoA).

Evaluations at the ESID visit showing abnormal results indicating a possible causal relationship with the study intervention must be followed by the investigator (as often as deemed prudent) until satisfactory clinical resolution or stabilization. Certain long-term adverse events of anti-retroviral therapy (ART) cannot be followed to resolution within the setting of this protocol; in these cases, follow-up will be the responsibility of the treating physician, which will be agreed upon with the sponsor's medical monitor.

Safety will be evaluated throughout the study from the time a signed and dated informed consent form (ICF) is obtained until completion of the participant's last study-related activity.

8.2.1. Physical Examination

A complete physical examination will be conducted at the time points in the Schedule of Activities (SoA). Complete physical examinations include general appearance; skin (and mucus membranes); eyes; ears, nose, and throat; head, neck, and thyroid; heart; lung, chest (incl. breasts); abdomen; genitalia; anorectal; lymph nodes; musculoskeletal; and neurological. Urogenital/anorectal examination will be performed at the discretion of the investigator if clinically relevant. Participants should be undressed during the complete physical examinations, which should be performed by a licensed medical doctor, physician's assistant or nurse practitioner in accordance with local guidelines. Physical examination will also include evidence of ascites or encephalopathy at Screening in order to fully calculate Child Pugh Class.

Symptom directed physical examinations may be conducted at all other scheduled and unscheduled study visits based on reported safety or tolerability issues.

8.2.2. Vital Signs

Pulse/heart rate (supine after at least 5 minutes rest) and blood pressure will be assessed will be conducted at all study visits.

Blood pressure and pulse/heart rate measurements should be preceded by at least 5 minutes of rest in a quiet setting without distractions (eg, television, cell phones).

8.2.3. Electrocardiogram (ECG)

Not applicable

8.2.4. Clinical Safety Laboratory Assessments

Blood samples for serum chemistry and hematology and a urine sample for urinalysis will be collected as noted in Appendix 2: Clinical Laboratory Tests and Calculations. All clinical laboratory testing will be performed by the central laboratory and results will be sent to the investigator. The investigator must review the laboratory results, document this review, and record any clinically relevant changes occurring during the study in the AE section of the CRF. The laboratory reports must be filed with the source documents.

The central laboratory will send the investigator and sponsor an alert form whenever a Grade 3 or Grade 4 laboratory abnormality (see Appendix 7: DAIDS Table for Grading the Severity of Adult

63

and Pediatric Adverse Events) is observed. In case a Grade 3 or Grade 4 laboratory abnormality occurs, a confirmatory test should be performed preferably within 72 hours after the results have become available, before study intervention interruption or discontinuation, unless such delay is not consistent with good medical practice.

If a Grade 3 or Grade 4 laboratory abnormality is well documented before the start of the study and not considered a safety concern by the investigator, a confirmatory retest is not mandatory. The following laboratory abnormalities do not warrant mandatory confirmation:

- Asymptomatic Grade 3 or Grade 4 glucose elevations in participants with pre-existing diabetes.
- Asymptomatic Grade 3 or Grade 4 triglyceride or cholesterol elevations.

For more details on the management of Grade 3 and 4 laboratory toxicities that occur during the open-label treatment phase, see Section 8.2.6, and Appendix 6: Management of Clinically Significant Laboratory Toxicities.

8.2.5. Patient-reported Outcomes

Following PROs will be assessed at the time points indicated in the Schedule of Activities (SoA), (Appendix 8: Patient Reported Outcomes Questionnaires). Participants will complete the PROs using the sponsor-provided electronic devices. Study site personnel will train the participants on how to use the electronic device. All PRO assessments will be done in English-speaking and Spanish-speaking participants.

The BSQ-8D, HIV-SI and PGIC (including PGIC-S) should be completed by the participants during the study visit before all other study-related procedures to prevent influencing participant perceptions. The PGIC and PGIC-S should be completed after the participant completes the BSQ-8D and HIV-SI.

8.2.5.1. HIV-Symptom Index (HIV-SI)

The HIV-SI is a validated PRO instrument that assesses the burden of 20 common symptoms associated with HIV treatment or disease. Respondents are asked about their experience with each of 20 symptoms during the past 4 weeks using a 5-point, Likert-type scale. Response options and scores are as follows: (0) "I don't have this symptom;" (1) "I have this symptom and it doesn't bother me;" (2) "I have this symptom and it bothers me a little;" (3) "I have this symptom and it bothers me;" (4) "I have this symptom and it bothers me a lot." The 20 symptoms comprising the HIV-SI are fatigue/loss of energy, difficulty sleeping, nervous/anxious, diarrhea/loose bowels, changes in body composition, feeling sad/down/depressed, bloating/pain/gas in stomach, muscle aches/joint pain, problems with sex, trouble remembering, headaches, pain/numbness/tingling in hands/feet, skin problems/rash/itching, cough/trouble breathing, fever/chills/sweats, dizzy/lightheadedness, body weight loss/wasting, nausea/vomiting, hair loss/changes, and loss of appetite/food taste. Symptoms scores can be dichotomized into not bothersome (scores of 0 or 1) or bothersome (scores of 2, 3 and 4) and overall bothersome symptom count at baseline can be generated by counting the number of individual symptoms scored as bothersome.¹³

8.2.5.2. Body Shape Questionnaire (BSQ-8D)

The BSQ-8D is an 8-item version of the 34-item self-report questionnaire that was developed and validated to measure concerns about body shape; in particular, it focused on the phenomenal experience of "feeling fat". ^{9,16} Respondents are asked about how they have been feeling about their appearances over the past four weeks. Each item from this questionnaire is answered using a 6-point Likert scale: 1 (never), 2 (rarely), 3 (sometimes), 4 (often), 5 (very often), and 6 (always) and the overall score is the total across the 8 items.

8.2.5.3. **DAILY EATS**

The DAILY EATS will be administered to measure eating-related concepts such as hunger, appetite, cravings, and satiety. The home-based DAILY EATS should be completed daily, preferably in the evening, and, whenever possible, in the same setting for 7 consecutive days. The site should contact participants approximately 7 days prior to the Baseline (Day 1), Week 24 and Week 48 visits, preferably by telephone, to remind the completion of the DAILY EATS for 7 consecutive days prior to the applicable visit. For participants who discontinue early from study intervention, no DAILY EATS completion is required at the ESID visit.

8.2.5.4. Patient Global Impression of Change

The PGIC is a global index that is used to rate the overall status of the participant related to the participant's overall condition. It is rated by the participant and is based on the single question, "Compared to before starting the study or compared to the Week 24 visit, my overall status is," where response choices include 1 very much improved, 2 much improved, 3 minimally improved, 4 no change, 5 minimally worse, 6 much worse, and 7 very much worse.

The single-item PGIC for satiety (PGIC-S), with question, "Compared to before starting the study or compared to the Week 24 visit, how would you rate your satisfaction (fullness) after meals in the past 7 days?" and where response choices include 1 much more satisfied (full), 2 moderately more satisfied (full), 3 a little more satisfied (full), 4 no change, 5 a little less satisfied (full), 6 moderately less satisfied (full), and 7 much less satisfied (full), will also be used. The content validity of the PGIC-S has been demonstrated in overweight and obese patients with and without T2DM, although the psychometric properties of the PGIC-S were not evaluated.

8.2.6. Toxicity Management

The toxicity management guidelines in this section are applicable throughout the entire study starting from when the participant starts study intervention through the study period.

General guidance for the management of toxicities is provided in Section 8.2.6. Guidance for specific toxicities is provided in Sections 8.2.6.1 through 8.2.6.8. In addition, see Section 8.2, Safety Assessments, Appendix 4: Adverse Events: Definitions and Procedures for Recording, Evaluating, Follow-up, and Reporting, and Appendix 6: Management of Clinically Significant Laboratory Toxicities. Questions regarding toxicity management should be directed to the sponsor's medical monitor.

8.2.6.1. General Guidance for the Management of Clinical Events and Laboratory Abnormalities

Grade 1 and 2

Continue study intervention at the discretion of the investigator.

Grade 3

- For a Grade 3 clinical event or clinically relevant laboratory abnormality, study intervention may be continued if the event is considered to be unrelated to study intervention.
- For a Grade 3 clinical event, or clinically relevant laboratory abnormality confirmed by repeat testing (see Section 8.2), that is considered related to study intervention, study intervention should be withheld until the toxicity returns to baseline or within 1 grade from baseline, ie, ≤Grade 2.
- Mandatory confirmation is not warranted for asymptomatic Grade 3 glucose elevations in participants with preexisting diabetes, and for asymptomatic Grade 3 triglyceride or cholesterol elevations.
- If a laboratory abnormality recurs to ≥Grade 3 following rechallenge with study intervention and is considered to be related to study intervention, study intervention should be permanently discontinued, and the participant managed according to local practice. Recurrence of laboratory abnormalities considered unrelated may not require permanent discontinuation.

Grade 4

- For a Grade 4 clinical event or clinically relevant laboratory abnormality confirmed by repeat testing (see Section 8.2), that is considered related to study intervention, study intervention should be permanently discontinued, and the participant managed according to local practice. The participant should be followed as clinically indicated until the laboratory abnormality returns to baseline or is otherwise explained, whichever occurs first. A clinically relevant Grade 4 laboratory abnormality that is not confirmed upon repeat testing should be managed according to the algorithm for the new toxicity grade.
- Mandatory confirmation is not warranted for asymptomatic Grade 4 glucose elevations in participants with preexisting diabetes, and for asymptomatic Grade 4 triglyceride or cholesterol elevations.
- Study intervention may be continued without dose interruption for a clinically nonrelevant Grade 4 laboratory abnormalities (eg, Grade 4 creatine phosphokinase after strenuous exercise, or triglyceride elevation that is nonfasting or that can be medically managed), or a clinical event considered unrelated to study intervention.

A schematic overview of these guidelines is provided in Appendix 6: Management of Clinically Significant Laboratory Toxicities.

8.2.6.2. Cutaneous Events/Rash

Darunavir is a sulfonamide. Participants who previously experienced sulfonamide allergy will be allowed to enter the study. To date, no potential for cross-sensitivity between drugs in the sulfonamide class and DRV has been identified.

CONFIDENTIAL – FOIA Exemptions Apply in U.S. Status: Approved, Date: 29 April 2022

Cutaneous events/rash should be captured in the AE section of the eCRF.

Management of cutaneous events/rash will be at the discretion of the investigator, taking into account the following protocol procedures (see also Table 1), and should follow generally accepted medical standards. Cetirizine, levocetirizine, topical corticosteroids, and antipruritic agents will be allowed at the investigator's discretion for treatment of all grades of rashes.

Grade 1 and 2 Cutaneous Reaction/Rash

A Grade 1 cutaneous reaction/rash is defined as localized rash. A Grade 2 cutaneous reaction/rash is defined as diffuse rash or target lesions.

Participants experiencing a Grade 1 or 2 rash or cutaneous event may continue treatment or have their study intervention interrupted at the investigator's discretion. Safety sampling (processed by the central laboratory) at the time of the rash and clinical follow-up for these AEs will be at the discretion of the investigator; however, close clinical follow-up is recommended to monitor for any progression of the adverse event.

Grade 3 and 4 Cutaneous Reaction/Rash

A Grade 3 cutaneous reaction/rash is defined as:

- Diffuse rash with vesicles or limited number of bullae or superficial ulceration of mucous membrane limited to 1 site.
- For the purpose of this study, the sponsor considers qualifying as a Grade 3 rash:
- Cutaneous reaction/rash with at least 1 of the following:

elevations of ALT/AST >2× baseline but ≥5×ULN

fever ≥38°C or 100°F

serum sickness-like reaction

eosinophil count >1,000/mm³

• The syndromes of drug rash with eosinophilia and systemic symptoms (DRESS) and acute generalized exanthematous pustulosis (AGEP)

A Grade 4 cutaneous reaction/rash is defined as:

- Extensive or generalized bullous lesions
- Stevens-Johnson syndrome (SJS)
- Ulceration of mucous membrane involving at least 2 distinct mucosal sites
- Toxic epidermal necrolysis (TEN)

Participants experiencing a Grade 3 or 4 rash or cutaneous event must have their study intervention discontinued. Referral to a dermatologist and biopsy are required for these events preferably within 24 hours after the site becomes aware of the cutaneous event/rash.

Safety testing (to be processed by the central laboratory) of the following parameters is required to determine possible liver or systemic abnormalities: ALT, AST, bilirubin (total, direct and indirect), creatinine and a hematology profile. Close clinical follow-up and appropriate medical intervention should be instituted for these events; daily follow-up is recommended for 5 days from the onset of the event to monitor for progression of the event and weekly afterwards as long as Grade 3 or 4 rash is present. Once Grade 3 or 4 rash has resolved to ≤Grade 2 rash, follow-up should be done according to the instructions for Grade 1 or 2 rash.

Table 1: Summary of Cutaneous Reaction/Rash Follow-up

DAIDS Toxicity Grade	Definitions	Investigator Action
Grade 1	Localized rash	Participant may continue study intervention
Grade 2	Diffuse rash Target lesions	Participant may continue study intervention
Grade 3	Diffuse rash with vesicles or limited number of bullae	Permanently discontinue study intervention
	Superficial ulcerations of mucous membrane limited to 1 site For the purpose of this protocol, the sponsor considers qualifying as a Grade 3 rash the following: Cutaneous reaction/rash with at least 1 of the following: - Elevations in alanine aminotransferase (ALT) and/or aspartate aminotransferase (AST) (>2× baseline but ≥5× upper limit of normal range (ULN) - Fever ≥38°C or 100°F - Serum sickness-like reaction - Eosinophils>1,000/mm³	Referral to a dermatologist and biopsy, preferably within 24 hours after the site becomes aware of the cutaneous event/rash Laboratory assessments need to be performed
Grade 4	Extensive or generalized bullous lesions Stevens-Johnson syndrome (SJS) Ulceration of mucous membrane involving at least 2 distinct mucosal sites Toxic epidermal necrolysis (TEN)	Permanently discontinue study intervention Referral to a dermatologist and biopsy, preferably within 24 hours after the site becomes aware of the cutaneous event/rash Laboratory assessments need to be performed

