When selecting a primary AE term to report, sites should select the term that best describes what

occurred to the participant. For example, a participant may present with itching, urticaria, flushing, angioedema of the face, and dyspnea. If the underlying diagnosis is determined to be an acute allergic reaction, sites should report "Acute Allergic Reaction" as the primary AE term.

Determining Severity Grade for Parameters between Grades

If the severity of an AE could fall in either one of two grades (i.e., the severity of an AE could be either grade 2 or grade 3), sites should select the higher of the two grades.

Estimating Severity Grade for Parameters Not Identified in the Grading Table

The functional table below should be used to grade the severity of an AE that is not specifically identified in the grading table. In addition, all deaths related to an AE are to be classified as grade 5.

PARAMETER	GRADE 1 MILD	GRADE 2 MODERATE	GRADE 3 SEVERE	GRADE 4 POTENTIALLY LIFE- THREATENING
Clinical adverse event NOT identified elsewhere in the grading table	Mild symptoms causing no or minimal interference with usual social & functional activities with intervention not indicated	Moderate symptoms causing greater than minimal interference with usual social & functional activities with intervention indicated	Severe symptoms causing inability to perform usual social & functional activities with intervention or hospitalization indicated	Potentially life threatening symptoms causing inability to perform basic self care functions with intervention indicated to prevent permanent impairment, persistent disability, or death

Major Clinical Conditions Cardiovascular

PARAMETER	GRADE 1 MILD	GRADE 2 MODERATE	GRADE 3 SEVERE	GRADE 4 POTENTIALLY LIFE- THREATENING	
Arrhythmia (by ECG or physical examination) Specify type, if applicable	No symptoms AND No intervention indicated	No symptoms AND Non urgent intervention indicated	Non life threatening symptoms AND Non urgent intervention indicated	Life threatening arrhythmia OR Urgent intervention indicated	

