Acute Allergic Reaction	Localized unticaria (wheals) with no medical intervention indicated	Localized urticaria with intervention indicated OR Mild angioedema with no intervention indicated	Generalized urticaria OR Angioedema with intervention indicated OR Symptoms of mild bronchospasm	Acute anaphylaxis OR Life threatening bronchospasm OR Laryngeal edema
Chills	Symptoms causing no or minimal interference with usual social & functional activities	Symptoms causing greater than minimal interference with usual social & functional activities	Symptoms causing inability to perform usual social & functional activities	NA
Cytokine Release Syndrome ⁸	Mild signs and symptoms AND Therapy (i.e., antibody infusion) interruption not indicated	Therapy (i.e., antibody infusion) interruption indicated AND Responds promptly to symptomatic treatment OR Prophylactic medications indicated for ≤ 24 hours	Prolonged severe signs and symptoms OR Recurrence of symptoms following initial improvement	Life threatening consequences (e.g., requiring pressor or ventilator support)
Fatigue or Malaise Report only one	Symptoms causing no or minimal interference with usual social & functional activities	Symptoms causing greater than minimal interference with usual social & functional activities	Symptoms causing inability to perform usual social & functional activities	Incapacitating symptoms of fatigue or malaise causing inability to perform basic self care functions
Fever (non axillary temperatures only)	38.0 to < 38.6°C or 100.4 to < 101.5°F	≥ 38.6 to < 39.3°C or ≥ 101.5 to < 102.7°F	≥ 39.3 to < 40.0°C or ≥ 102.7 to < 104.0°F	≥ 40.0°C or ≥ 104.0°F
Pain ⁹ (not associated with study agent injections and not specified elsewhere) Specify location	Pain causing no or minimal interference with usual social & functional activities	Pain causing greater than minimal interference with usual social & functional activities	Pain causing inability to perform usual social & functional activities	Disabling pain causing inability to perform basic self care functions OR Hospitalization indicated

Befinition: A disorder characterized by nausea, headache, tachycardia, hypotension, rash, and/or shortness of breath.

CONFIDENTIAL - FOIA Exemptions Apply in U.S.

For pain associated with injections or infusions, see the Site Reactions to Injections and Infusions section (page 23).

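### The fever limit that turns a rash into Grade 3 is printed as 38°C or 100°F, so this mandatory-stop threshold is not the same temperature in both units

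*Protocol*

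**What the plan says.** Section 8.2.6.2 of the protocol (Cutaneous Events/Rash) adds sponsor-defined features to the DAIDS rash grades. Any one of them together with a rash makes the event Grade 3. One of them is "fever ≥38°C or 100°F". The Grade 3 row of Table 1 repeats the same pair: "Fever ≥38°C or 100°F - Serum sickness-like reaction".

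The grade decides what happens to the participant:

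- Below Grade 3: "Participants experiencing a Grade 1 or 2 rash or cutaneous event may continue treatment", or have it interrupted, at the investigator's discretion.
- Grade 3 or 4: "Participants experiencing a Grade 3 or 4 rash or cutaneous event must have their study intervention discontinued", and "Referral to a dermatologist and biopsy are required for these events". Table 1 makes the discontinuation permanent.

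Two other places bear on the reading, both in Appendix 7. Its general guidance says that where severity could fall in either of two grades, "sites should select the higher of the two grades". Its fever row gives Grade 1 as "38.0 to < 38.6°C or 100.4 to < 101.5°F" and Grade 2 as "≥ 38.6 to < 39.3°C or ≥ 101.5 to < 102.7°F".

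**The concern.** A single cut-off expressed in two units should be one temperature. Here it is two. A site that reads 37.9°C sees a value below the printed Celsius limit. A site that reads the same temperature as 100.2°F sees a value above the printed Fahrenheit limit. If no other Grade 3 feature is present, the first site may leave the participant on treatment, while the second must stop treatment for good and arrange a referral and biopsy.

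What is at stake is consistent handling of a hard rule. The general Grade 3 guidance in section 8.2.6.1 lets treatment continue when the event is judged unrelated. The rash section states no such exception, so the temperature limit can decide the outcome by itself. Rash is also an expected event: section 2.3.2 lists it among the most common adverse drug reactions, at rates of at least 1 in 10.

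**Working it through.** **Inputs.** The printed pair, 38°C and 100°F (section 8.2.6.2 and Table 1), and the fever row of the DAIDS table in Appendix 7. The second limit carries no inequality sign of its own; it is read here as at or above 100°F.

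**Formulas.** F = C × 9/5 + 32, and C = (F − 32) × 5/9.

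**Can the printed pair be reproduced?**

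- 38 × 9/5 + 32 = 100.4°F, not 100°F.
- (100 − 32) × 5/9 = 37.78°C, not 38°C.
- Rounded to whole degrees, 100.4 becomes 100 and 37.78 becomes 38.

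The pair is therefore what whole-degree rounding gives. It is not matched by exact conversion or at one decimal.

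**Size of the gap.** 100.4 − 100 = 0.4°F, and 38 − 37.78 = 0.22°C.

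**Readings that fall between the limits, to one decimal.**

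| Reading | Converted | Meets 100°F | Meets 38°C |
|---|---|---|---|
| 37.7°C | 99.86°F | no | no |
| 37.8°C | 100.04°F | yes | no |
| 37.9°C | 100.22°F | yes | no |
| 38.0°C | 100.4°F | yes | yes |

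Two Celsius readings (37.8 and 37.9) and four Fahrenheit readings (100.0, 100.1, 100.2 and 100.3) lie in the band.

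**Check against Appendix 7.** The boundaries in the fever row convert as follows: 38.0°C = 100.4°F (printed 100.4), 38.6°C = 101.48°F (printed 101.5), 39.3°C = 102.74°F (printed 102.7) and 40.0°C = 104.0°F (printed 104.0). All four agree to one decimal. The protocol therefore holds a correctly matched pair for 38.0°C elsewhere. Those decimals also survived the PDF reading, and the rash pair appears twice in the same form, so a decimal lost in extraction is unlikely.

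**The case against.** The best answer is that the text is not ambiguous. Two limits joined by an or have one literal meaning: a temperature that meets either one qualifies, so 100°F governs and the 38°C limb is redundant. A site at 37.9°C that converts its reading gets 100.2°F and should grade the rash as 3. The higher-grade rule in Appendix 7 points the same way. On that view the protocol claims no equivalence, and the fault is untidy drafting of a rule that errs toward stopping the drug.

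Most of this stands. The literal reading is determinate and cautious. It still does not give one temperature in both units. A Celsius reader who sees 37.9 against a printed 38 has no evident reason to convert, and sees no tie for the higher-grade rule to break.

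It is also fair to say that the split may rarely arise. Several details suggest a United States study: US Prescribing Information in section 6.1, the US background radiation comparison in section 4.2.1, and the state of residence in SAP Table 3. If every site reads Fahrenheit, every site applies 100°F. That is inference, because I found no instruction that fixes a thermometer unit.

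A reader might go further and infer that 100.4°F must be the intended limit because Appendix 7 pairs it with 38.0°C. The documents do not support that. The row grades fever as an adverse event in its own right, for non-axillary temperatures, and does not define the sponsor's rash rule. It shows the correct unit pair, not which cut-off the sponsor meant.

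**Conclusion.** The point holds as a minor correction. The two printed limits differ by 0.4°F (0.22°C), so a rule that forces permanent discontinuation, referral and biopsy does not have the same threshold in both units. It can change handling only for a rash with no other Grade 3 feature and a temperature of 100.0 to 100.3°F (37.8 to 37.9°C), and only where a site applies the Celsius limb alone. The documents give no frequency for this. The Schedule of Activities lists blood pressure and pulse as the vital signs, so the relevant readings would mostly be those taken when a rash is assessed.

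Two stronger conclusions might be inferred, and neither is supported. One is that participants are less safe as the rule is written: the literal limit is the lower one, and below Grade 3 the investigator may still interrupt treatment. The other is that the trial's results are affected: nothing in the documents shows an effect on the primary analysis, and sample size, power and type I error do not depend on this threshold.

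The verdict assumes that the 100°F limb means at or above, and that temperatures are recorded to one decimal.

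**What to change.** Ask the sponsor which cut-off was intended, then print one matched pair in both section 8.2.6.2 and the Grade 3 row of Table 1:

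- **≥38.0°C (≥100.4°F).** This agrees with the unit pair in the Appendix 7 fever row. Its drawback is that it raises the literal limit from 100.0°F to 100.4°F, which makes a mandatory stop slightly less cautious.
- **≥37.8°C (≥100°F).** This keeps the current literal threshold. The two values agree to one decimal (37.8°C = 100.04°F).

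The choice is clinical and belongs to the sponsor; either option removes the mismatch. The work is two text edits, but the change is not free of process. Appendix 3 requires a formal sponsor amendment, investigator signature and prior IEC/IRB approval for anything beyond logistic or administrative changes, and a discontinuation threshold is hard to call administrative. It is best carried in the next protocol amendment, not issued alone.
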